Implementation activities. Foundational REP activities have been described previously. After 6 months, sites that did not meet adoption benchmarks and were enrolled in the CRT (n=25) will either continue with foundational REP (n=12) or receive higher intensity implementation support (n=13). Continuing foundational REP for half of the sites is a reasonable approach because we cannot anticipate whether VAMCs that do not adopt Caregiver FIRST within the first 6 months

simply need a) more time given competing priorities or other reasons or b) a more intensive approach. Higher intensity implementation support over a period of approximately 4 months will consist of a needs assessment survey to assess barriers to implementation and approximately 3 to 4 facilitated group modules provided by Function QUERI and VA CSP to promote interactive problem solving in the context of a supportive interpersonal relationship.

Caregiver/Veteran participants. Targets for participation in Caregivers FIRST are family or friend caregivers of Veterans with functional and/or cognitive impairment, along with caregivers who have been identified as needing training, education and support (by Caregiver Support Program or others). The target class size for each round of the program is approximately 10-12 caregivers of Veterans, which would yield approximately 20-24 caregivers being trained per 6-month period if the recommended 2 rounds of classes are administered.

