Outcomes. Implementation outcomes. Adoption is a cluster-level dichotomous outcome defined as meeting a threshold of four or more training classes delivered to a minimum of five caregivers over a cumulative 12-month period (yes) or not meeting this threshold is considered non-adoption (no). In addition, while 12 months is the primary endpoint, penetration and fidelity outcomes will also be assessed over 6- and 18-month time periods with descriptive results. Penetration (primary outcome) defined as the (1) proportion of caregivers who received consults for VA caregiver education and training services who attended at least one class at a medical center over a 12-month period and (2) the number of classes delivered over a 12-month period. Fidelity outcomes are cluster-level defined as (1) the proportion of the number of recommended classes delivered over a 12-month period, (2) the number of caregivers who attended at least one class over a 12-month period, and (3) the mean number of classes attended per caregiver over a 12-month period. Effectiveness outcomes/ Quality metrics. Effectiveness outcomes will include Veteran days in the community (e.g., not in a hospital or nursing home) over a 6 month period after caregiver participation in Caregivers FIRST. We will use the inclusion of Caregivers FIRST in VA medical center performance plans as the quality metric, where sites report the status on meeting requirements within the CSP Program of General Caregiver Support Services (PGCSS). In addition, we will evaluate the number of caregivers enrolled with each site's PGCSS and whether the quality metrics change based on the implementation approach.

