community (home time) over a 6-month period. Our sample of Veterans for this analysis will come from sites that adopt Caregivers FIRST nationally (that is, not limited to the 25 enrolled sites). The sample of Veterans (approximately 20,000) will be from those whose caregiver received consults for VA caregiver education and training services, including to Caregivers FIRST over a year period after the program was announced as a minimum standard; some of those caregivers will attend Caregivers FIRST classes (i.e., treatment group) and some will not (i.e., comparison group). Data sources include CDW, VA/CMS repository data, Caregiver Support Program Data, and Geriatrics and Extended Care Data Analysis Center (GECDAC) Residential History File data. We will use inverse-probability of treatment weighted methods to adjust for confounding and estimate an average causal treatment effect for Caregivers FIRST on home time over the 6-month time period following the consult for a VA caregiver education and training. We use the same modeling approach described above to examine the effect of implementation approach on general program quality scores and size of the general caregiver program. In exploratory analysis, we are interested in assessing the impact of Caregivers FIRST on Veteran's days in the community over a 6-month period. Our sample of Veterans for this analysis will come from sites that adopt Caregivers FIRST. The sample of Veterans will be from those whose caregiver received consults for VA caregiver education and training services, including to Caregivers FIRST over a year period; some of those caregivers will attend Caregivers FIRST classes (i.e. treatment group) and some will not (i.e. comparison group). We will use inverse-probability of treatment weighted methods to adjust for confounding and estimate an average causal treatment effect for Caregivers FIRST on home time over the 6month time period following the consult for a VA caregiver education and training. The study team will determine a priori which covariates are likely to be key determinants of attending Caregivers FIRST training. We will explore the distribution that best fits the days at home outcome: Poisson, Negative Binomial, or zero-inflated. Generalized linear models with inverse propensity score weights will be used. We will describe the quality metrics using descriptive statistics, but these will not be modeled. Qualitative data collection and approaches to data integration have been described previously. To address the key questions: What are the costs for delivering one round of Caregivers FIRST training? What are the costs of the high- and lowintensity implementation support? The business case will include a budget impact analysis to help VA administrators consider the cost of implementation and delivery along with the effectiveness of the intervention in the context of the VA priorities to improve Veteran outcomes. The budget impact analysis will evaluate implementation costs for each strategy and intervention delivery costs per participant. The high-touch implementation support strategy is expected to use more resources (delivery time and attendance time) and potentially improve implementation outcomes, for example improved fidelity or increased penetration. To assess the value of the additional investment in implementation support, we will describe implementation costs per enrolled participant for each implementation strategy. While the overall resource use might be higher, a lower cost per participant would indicate a high value. We will use staff time and equipment data from the adaptations survey (baseline, 6 months, and 12 months) to assess costs using U.S. Veterans Health Administration salary and managerial cost accounting data. Drawing from methods in prior Function QUERI work, Business Case Analysis (BCA) will frame affordability to VA. For the cumulative 12-month study period, two types of costs will be collected for each site using a standardized method to track implementation activities 1) clinical delivery team costs incurred and 2) implementation strategy costs incurred. Because the 25 sites enrolled will represent a fraction of the sites nationally who will also implement (expect over 100 to implement), we can extrapolate to a national scenario in the BCA.

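### The exploratory Caregivers FIRST home-time analysis has two start dates, and the consult version forms its groups by later attendance with no stated window, which can bias the estimate

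*Combined protocol and SAP*

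**What the plan says.** Implementation Project 3, Outcomes, counts home time "over a 6 month period after caregiver participation in Caregivers FIRST". The measure is "Veteran days in the community (e.g., not in a hospital or nursing home"); how days after death count is not stated.

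Implementation Project 3, Analyses, uses a different start. It estimates the effect "on home time over the 6-month time period following the consult", and says so twice. The Caregivers FIRST text under Data Analysis and Statistical Considerations repeats the consult start. The cohort is about 20,000 Veterans whose caregivers had a consult during a one-year period. Groups follow attendance: "some of those caregivers will attend Caregivers FIRST classes (i.e., treatment group) and some will not (i.e., comparison group").

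The adjustment is inverse-probability-of-treatment weighting, and the aim is to "estimate an average causal treatment effect for Caregivers FIRST". On covariates: "The study team will determine a priori which covariates are likely to be key determinants of attending Caregivers FIRST training". No time-varying exposure, landmark or grace period is described.

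Attendance periods do appear under Outcomes, but for site-level measures. Penetration counts caregivers who "attended at least one class at a medical center over a 12-month period", and penetration and fidelity are also described over 6 and 18 months. None of these periods is tied to the home-time groups. Specific Aim 2 is labelled exploratory.

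**The concern.** The two start dates define different outcomes. A start at participation gives no six-month period for a Veteran whose caregiver never participates.

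The consult start gives everyone an index date but uses later information to form the groups. To be classed as an attender, the caregiver must reach a class. If the Veteran's death or placement before the class stops that, the Veteran is counted as a non-attender with a short home time, and attenders are credited with event-free waiting time. This is immortal-time bias, and it arises even when the programme does nothing. With no window, a caregiver could also first attend after the six-month outcome period has ended and still count as treated.

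The result is to be reported as an average causal effect, and the business case is meant to help administrators weigh cost alongside effectiveness. The programmer must settle the start date and window at some point, and settling them after seeing outcomes would be worse.

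**Working it through.** **No plan figure to reproduce.** The documents give no effect size, event rate, attendance share or consult-to-class interval for this analysis, only the approximate sample of 20,000. The calculation below is therefore an illustration with no programme effect.

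**Inputs (all assumed except T and n).**
- T = 182 days, the six-month outcome period; n = 20,000.
- Permanent loss of home time at p = 1, 2 or 3% per month of 30.4 days, half deaths and half placements. The daily rate is λ = −ln(1−p)/30.4.
- 30% of caregivers intend to attend, independently of risk, so weighting on consult-time covariates would change nothing.
- The wait W from consult to class is uniform on 0 to w days. The plan mentions "approximately 20-24 caregivers being trained per 6-month period if the recommended 2 rounds of classes are administered". Evenly spaced rounds would start every 182/2 = 91 days, so w = 90 is the central case; w = 14 and w = 180 show the range.

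**Formulas, consult version.** E is the time to loss and H = min(E, T).
- Overall mean: M = (1−e^(−λT))/λ.
- Chance of being event-free at class: S = (1−e^(−λw))/(λw).
- Home time carried by those event-free at class: N = mean over W of e^(−λW)·[W + (1−e^(−λ(T−W)))/λ].
- Death or placement blocks: attender mean N/S, attending share a = 0.3·S.
- Only death blocks: attender mean [(N+M)/2]/[(1+S)/2], share a = 0.3·(1+S)/2.
- Comparison mean: (M − a × attender mean)/(1−a).

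**Worked case, p = 2%, w = 90.** λ = 0.0202/30.4 = 0.000665; M = 171.42; S = 0.9707.
- Death or placement blocks: attenders 175.70; a = 0.2912; comparison (171.42 − 0.2912×175.70)/0.7088 = 169.67. False gain about 6.0 days.
- Only death blocks: attenders 173.53; a = 0.2956; comparison (171.42 − 0.2956×173.53)/0.7044 = 170.54. False gain 2.99 days.
- Neither blocks: attendance is unrelated to events, so the difference is 0.

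**False gain in days out of 182, at 1/2/3% monthly loss**

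| Wait | Only death blocks | Death or placement blocks |
|---|---|---|
| 0-14 days | 0.28 / 0.55 / 0.81 | 0.57 / 1.11 / 1.62 |
| 0-90 days | 1.55 / 2.99 / 4.33 | 3.12 / 6.04 / 8.78 |
| 0-180 days | 2.46 / 4.70 / 6.73 | 4.97 / 9.58 / 13.85 |

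Simulation of 4 million Veterans per scenario agrees to about 0.1 day.

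**Compared with sampling error.** At 2%, the SD of H is 34.4 days. With about 5,986 attenders and 14,014 others (w = 14, only death blocks), SE = 34.4×√(1/5,986 + 1/14,014) = 0.53. The gain of 0.55 gives z of about 1.0, within noise. For w = 90, 2.99/0.53 gives z of about 5.6. Both ignore weighting and site clustering.

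**Sensitivity (simulation, waits 0-90).**
- Days after death counted as home: 0.0/−0.1/−0.2 if only death blocks; 1.6/3.0/4.4 if both block.
- 90% of placements reversed after a mean of 30 days: 1.9/3.7/5.5 if both block; 1.5/3.0/4.5 if only death blocks.
- Intent to attend varied from 10 to 50% (at 2%): 4.8-8.3 if both block; 2.4-4.2 if only death blocks.
- Mixed starts (attenders from class, others from consult): +0.9/+1.8/+2.5 if both block; −0.8/−1.6/−2.4 if only death blocks. No passage specifies this hybrid; it shows only that the start date can change the sign.

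**Check of a landmark at day 90.** Classifying by attendance to day 90, among Veterans alive and at home then, and counting 182 days from there leaves a difference within 0.13 day of zero in every run. Requiring only that the Veteran be alive leaves 1.9/3.6/5.3 days when placement also blocks.

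**The case against.** Every analysis statement uses the consult, which both groups share. The Outcomes line may simply be loose wording, and the analysis text could govern. So a reader might infer that non-attenders have no index date anywhere, or that the plan cannot be programmed. The documents do not support either: the consult version gives a common start and can be run as written. What stands is that the two sections disagree and that the runnable version is the one exposed to the bias.

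A reader might also take 12 months as the plan's only attendance period and conclude that it exceeds the outcome period. It is not the only one: 6 and 18 months are given too, and 6 months equals the outcome period. The narrower point remains, because none of the three is linked to these groups.

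The weighting criticism rests partly on silence. Covariate choice is left to the team, and reading it as consult-time covariates is an inference. The privacy section lists referral, appointment, admission, discharge and death dates, so the data for handling timing are planned. The gap is in specification, not data. Even so, weights for who tends to attend do not correct for an event after the consult that prevents attendance.

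Finally, the analysis is exploratory, and the size of the shift rests wholly on assumed inputs. That is fair, and it limits how much weight the figures can carry. It does not make it sound to report a causal effect from groups defined by later attendance.

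**Conclusion.** The concern holds in a conditional form and should be fixed. Confidence is high for the conflict in start dates and for the condition under which bias arises: death or placement before class must make attendance less likely. Confidence in the size is low. Waits of 0-90 days give roughly 1.5 to 8.8 days under the stated assumptions. Waits of 0-14 days give 0.3 to 1.6 days, within noise when only death blocks attendance. The shift is about zero if such events do not affect attendance, or if only death does and days after death count as home, which the outcome definition leaves open.

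A reader might infer that the finished analysis will overstate the benefit by some known amount. The documents do not support that: they give no rates or waits, and residual confounding could add to the shift or offset it. Nor does the point reach the randomised comparison of implementation strategies, whose outcomes are measured at site level.

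**What to change.** Use the same time zero for both groups in the Outcomes and Analyses text of Implementation Project 3 and under Data Analysis and Statistical Considerations. Classify attendance within a fixed window that does not overlap the outcome period, and state how days after death count.

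One simple option is a landmark at the end of the window, restricted to Veterans alive and at home, with six months counted from there in both groups. The window length should be set from the observed consult-to-class interval before outcomes are examined. Sequential trials or clone-censor-weighting from the consult are alternatives that keep the wider population, but they need dated attendance and placement and more programming.

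**Cost.** The wording change is small, and the programming is modest on data sources already planned. A day-90 landmark would need records to day 90 + 182 = 272. It would drop 1−(1−p)^(90/30.4) = 2.9/5.8/8.6% of Veterans at the assumed rates, and its estimand is conditional on being at home at day 90. Caregivers who first attend after the window count as non-attenders, which dilutes any real effect. If waits run to 180 days, a day-90 landmark would misplace about half of all attenders (90/180), which is why the window should follow the observed interval.

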
Sample size estimate. Sample size calculations were conducted for the penetration implementation outcomes at 12-months. Based on a two-sided t-test based on a sample size of 25 sites (12 foundational REP and 13 higher intensity), a type-1 error rate of 5%, we will have 80% power to detect an effect size difference of 1.2 and 90% power to detect an effect size

difference of 1.4 between arms. We did not adjust alpha for co-primary outcomes as success will be assessed based on improvement in both measurements of penetration **Leadership**. [name] [name], health economist and health services researcher, evaluates delivery and costs of long-term services and supports, including interventions to support informal caregivers. She is the director of the QUERI Partnered Evaluation of the nationwide VA Caregiver Support Program (VA CARES) and the Function and Independence Scientific Core at the Durham COIN ADAPT.

Rapid Response Team

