Caregivers FIRST sample size estimate. Sample size calculations were conducted for the penetration implementation outcomes at 12-months. Based on a two-sided t-test based on a sample size of 25 sites (12 foundational REP and 13 higher intensity), a type-1 error rate of 5%, we will have 80% power to detect an effect size difference of 1.2 and 90% power to detect an effect size difference of 1.4 between arms. We did not adjust alpha for co-primary outcomes as success will be assessed based on improvement in both measurements of penetration. Analyses. To address the question: Are there differences in implementation outcomes (penetration, fidelity) at 6, 12, or 18 months between arms? We hypothesize that sites randomized to higher intensity strategies will achieve higher penetration and fidelity. As part of our type III effectiveness-implementation hybrid design framework, the primary research question compares differences in implementation outcomes (penetration, fidelity, and adoption) between implementation arms at 12 months. Implementation outcomes are continuous, count, and binary outcomes, and generalized linear models⁷⁵ will be used to examine the effect of high-touch support on implementation outcomes at 12 months. We will use generalized linear models⁷⁵ to examine the effect of implementation arm on implementation outcomes at 12months. The main predictor of interest will be enhanced (high touch) implementation support vs. foundational (low touch) implementation support, and stratification variables for site complexity (low complexity (2, 3, and no complexity) versus all others) and prior implementation of Caregivers FIRST or not will be included; other facility level covariates for consideration are CSP program quality score and size of CSP program. In secondary analyses, implementation outcomes over a 6-month and 18-month period will be assessed and described.. We will examine how implementation outcomes change over time using descriptive methods (e.g. plots, descriptive statistics, subgroups). Descriptive statistics for survey measures such as organizational readiness for implementation change will be calculated overall and by randomization arm. We will use the same modeling approach described above to examine the effect of the implementation strategy on survey measures. To address the guestion: What is the impact on effectiveness outcomes/quality metrics (quality of VA General Caregiver Program, Veteran days in the community) at implementing sites? We will assess the impact of Caregivers FIRST on Veteran days in the community (home time) over a 6-month period. Our sample of Veterans for this analysis will come from sites that adopt Caregivers FIRST nationally (that is, not limited to the 25 enrolled sites). The sample of Veterans will be from those whose caregiver received consults for VA caregiver education and training services, including to Caregivers FIRST over a year period after the program was announced as a minimum standard; some of those caregivers will attend Caregivers FIRST classes (i.e., treatment group) and some will not (i.e., comparison group). We will use inverse-probability of treatment weighted methods to adjust for confounding and estimate an average causal treatment effect for Caregivers FIRST on home time over the 6-month time period following the consult for a VA caregiver education

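### Caregivers FIRST: the stated 80% and 90% power is for one outcome, but success requires improvement on two

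*Combined protocol and SAP*

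**What the plan says.** Under Implementation Project 3, Outcomes, the primary outcome has two parts. The first is a proportion: "Penetration (primary outcome) defined as the (1) proportion of caregivers who received consults" and then attended at least one class. The second is a count: "the number of classes delivered over a 12-month period". The same paragraph fixes the time point: "while 12 months is the primary endpoint".

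The Sample size estimate for this project refers to these outcomes in the plural: "Sample size calculations were conducted for the penetration implementation outcomes at 12-months". It gives one calculation, a two-sided t-test at 5% with 12 foundational REP sites and 13 higher-intensity sites, and one pair of results. For the smaller effect it states "we will have 80% power to detect an effect size difference of 1.2"; for the larger effect it states "90% power to detect an effect size difference of 1.4 between arms". The reason for leaving alpha alone follows: "We did not adjust alpha for co-primary outcomes as success will be assessed based on improvement in both measurements of penetration".

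The Caregivers FIRST sample size estimate under Data Analysis and Statistical Considerations repeats the same design, figures and reason. Neither section gives a correlation between the two outcomes or a power for succeeding on both.

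**The concern.** A rule that requires success on every co-primary outcome controls type I error without splitting alpha, and the plan is entitled to rely on that. The price is power, because the trial fails if either test fails. The plan takes the benefit on alpha but does not count the cost.

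These are the only power figures for this trial. A reader who sets them beside the success rule will take the risk of missing a true effect of 1.2 to be 20%, when it may be nearer 23–33%. A null result would then be read as stronger evidence against the higher-intensity strategy than the design supports.

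**Working it through.** **Inputs from the plan.** n₁ = 12, n₂ = 13, two-sided α = 0.05 per outcome, standardised effect d = 1.2 or 1.4, success on both outcomes.

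**Assumptions not in the plan.** The correlation ρ between the two outcomes across sites; equal d on both, except where stated; and approximately normal site-level outcomes, which is rough for a proportion and a count.

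**Step 1: reproduce the stated power.** For a single t-test, df = 12 + 13 − 2 = 23, the critical value is 2.069, and the noncentrality is d × √(12 × 13 / 25) = 2.498d.

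- d = 1.2: noncentrality 3.00, power 81.9%.
- d = 1.4: noncentrality 3.50, power 91.7%.

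Exactly 80% and 90% need d = 1.17 and 1.36, so the plan's 1.2 and 1.4 look like these values rounded up. The stated figures are therefore correct for one outcome. The Overview of the implementation projects gives 24 sites rather than 25; with 12 and 12, single-test power is 80.2% and 90.6%, which changes nothing here.

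**Step 2: power on both, uncorrelated outcomes.** At ρ = 0, joint power is essentially the product of the two powers:

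- d = 1.2: 0.819² = 0.67.
- d = 1.4: 0.917² = 0.84.

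**Step 3: power on both, correlated outcomes.** This was simulated with bivariate normal mean differences and a pooled covariance on 23 df. Success means both two-sided 5% t-tests are significant in favour of higher intensity.

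| Effects on the two outcomes | ρ = 0 | 0.3 | 0.5 | 0.7 | 0.9 | 0.95 |
|---|---|---|---|---|---|---|
| 1.2 and 1.2 | 67% | 69% | 71% | 73% | 77% | 78% |
| 1.4 and 1.4 | 84% | 85% | 86% | 87% | 89% | 90% |

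For ρ from 0 to 0.9, the shortfall against the stated figure is 80 − 67 = 13 down to 80 − 77 = 3 points at 1.2, and 90 − 84 = 6 down to 90 − 89 = 1 point at 1.4. Joint power reaches 80% at d = 1.2 only when ρ is about 0.99, and 90% at d = 1.4 only when ρ is about 0.96.

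**Step 4: unequal effects.** With effects of 1.2 and 1.5, joint power is 78–82% for ρ from 0 to 0.95. With 1.2 and 1.0 it is 55–66%. Joint power can approach the power of the weaker outcome but cannot exceed it.

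**Step 5: effects detectable on both outcomes with 25 sites.** An equal effect of about 1.34 (ρ = 0) down to 1.24 (ρ = 0.9) gives joint 80%. About 1.50 down to 1.42 gives joint 90%.

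**The case against.** **No stated figure is wrong.** The plan quotes power to detect an effect and never says this is power to meet the success rule. That is true. The fault is that the figures are unlabelled, are introduced as covering both outcomes, and stand beside an explicit both-outcomes rule with nothing else offered.

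**Improvement is not defined as significance.** This is also true; the both-significant reading is inferred. Suppose success meant significance on one named measure and only a favourable direction on the other. Power would then be about 82% at 1.2 and 92% at 1.4, with no shortfall. But the alpha argument would fail: with an effect of 1.4 on the named measure and none on the other, success would be declared about 46–50% of the time, against about 2.5% when both must be significant. The plan's reason for not adjusting alpha therefore holds only under the reading used here.

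**Zero correlation is implausible.** A site that delivers no classes scores zero on both measures, and the trial enrols sites that missed the adoption benchmark. This has force, and the lowest figures should not be taken as the likeliest. Over correlations of 0.5 to 0.9, joint power is 71–77% at 1.2 and 86–89% at 1.4, so a shortfall remains. Nothing in the plan supports a correlation near 1.

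**The calculation is approximate anyway.** The primary analysis is a generalized linear model with stratification covariates, not a t-test. That limits the precision of every figure here, including the plan's own, but it does not remove the loss from requiring two successes.

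**Conclusion.** The concern holds. The stated 80% and 90% are right for each outcome taken alone and too high for the success rule that the plan uses to justify its unadjusted alpha. Under equal effects, approximate normality and a correlation of 0 to 0.9, the chance of succeeding on both is about 67–77% at 1.2 and 84–89% at 1.4. The gap is small if the outcomes are very highly correlated, and it can close if one effect is clearly larger than 1.2. It widens if one effect is smaller. The unadjusted alpha itself is not in dispute. The point should be fixed, but it does not undermine the design.

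**What to change.** Make the same changes in the Sample size estimate under Implementation Project 3 and in its repeat under Data Analysis and Statistical Considerations:

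1. Label 80% at 1.2 and 90% at 1.4 as power for each outcome separately.
2. Add the joint power over a stated range of correlations (about 67–77% at 1.2 and 84–89% at 1.4 for 0 to 0.9, equal effects). Alternatively, restate the effects detectable on both outcomes: about 1.24–1.34 for 80% and 1.42–1.50 for 90%, as the correlation falls from 0.9 to 0.
3. State that success means two-sided p < 0.05 in favour of higher-intensity support on both outcomes, fixed and dated before 12-month outcome data are examined.

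This takes no extra sites, data or analyses; the cost is a less favourable power statement. Item 3 sets a success rule, so its timing matters. Version 15 (5/16/2024) does not show whether 12-month data have already been examined. If they have, the revision should say so.
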